## FORM

[REDACTED]

## STATISTICAL ANALYSIS PLAN N° GDX-44-004

VERSION 1.0

DATED: 09JAN2018

Page 23 / 60

	Central Laboratory Biochemistry results not available	Laboratory data base	Non major
	Central Laboratory Hematology results not available	Laboratory data base	Non major
	Urinalysis not performed	Clinical data base	Non major
	Vital signs not measured	Clinical data base	Non major
	Vital sign result missing	Clinical data base	Non major
	ECG not performed/Performed but not in triplicate	Clinical data base	Non major
	ECG result missing	Central ECG data base	Non major
	Tolerance at injection site is not filled in for patient receiving the study product	Clinical data base	Non major
	No VAS completed in case of injection site pain	Clinical data base	Non major
Non respect of study's schedule and procedures	MRI examination not performed	Clinical data base	Major
	Time between the two MRI procedures is strictly greater than 14 days and less or equal to 21 days	Clinical data base	Non major
	Time between the two MRI procedures is strictly greater than 21 days	Clinical data base	Major
	Time between contrast media administration and 3-D GRE acquisition for Brain and T1WSE/TSE acquisition for spine is greater than 10 minutes	Clinical data base	Non major
	Two different MRI system manufacturer used for both assessments	Imaging data base	Non major
	Two different MRI system model used for both assessments	Imaging data base	Non major
	Two different MRI system software version used for both assessments	Imaging data base	Non major
	Two different magnetic field strength used for both assessments	Imaging data base	Non major
	Two different MRI machines used for both assessments	Monitoring	Non major
	MRI machine used not qualified	Monitoring	Non major
	MRI exam for subject of subset 2 performed prior investigator's qualification	Monitoring	Non major
	Time between contrast media administration and 3-D GRE acquisition for Brain and T1WSE/TSE for spine acquisition is different of more than 10 minutes but less than 30 minutes between the two MRI for a single patient	Clinical data base	Non major
	Time between contrast media administration and 3-D GRE acquisition for Brain and T1WSE/TSE for spine acquisition is different of more than 30 minutes between the two MRI for a single patient	Clinical data base	Major
	Time between screening visit and first contrast media administration is strictly greater than 7 days	Clinical data base	Non major

CONFIDENTIAL

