### 3.2 Study Duration

The study includes 5 visits: 1 screening visit, 2 MRI visits and 2 safety visits.

Subject eligibility will be determined at a screening visit performed up to 7 days prior to the first study MRI (the screening visit may occur the same day as visit 2 if all the inclusion/non-inclusion criteria are met).

Two MRI visits are to be performed, one session with P03277 administration and another session with MultiHance® administration. The interval between the 2 MR examinations is  $\geq$  2 days to avoid carryover effects but  $\leq$  14 days to minimize the risk of measurable disease progression or lesion evolution. Eligibility criteria will be checked prior to MRI procedures and confirmed via the IWRS to validate IMPs allocation.

Two safety visits will be performed during the study, one day after each MRI examination.

The minimum study duration per subject is 4 days and the maximum duration is 22 days.

The subject's participation is defined as the period from the screening visit (ICF signature) to the last study visit and defined in [Section 11](#) in case of premature discontinuation.

The study will be considered as completed once all the images collected for all the subjects will have been reviewed by all the independent blinded readers.

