### 5.3 Condition of Investigational Medicinal Product allocation

#### 5.3.1 *Investigational Product(s) Allocation / Randomization*

At visit 2, the subjects will be randomly assigned to one of the doses of P03277 and to one series of 2 MRIs performed each at two study visits separated by a wash out period of 2 days minimum up to 14 days. One series consists of the use of P03277 as contrast agent at visit 2 and MultiHance® at visit 4. The second series consists of the use of MultiHance® at visit 2 and P03277 at visit 4.

The P03277 dose to be injected to the subjects will be attributed by randomization (according to randomization list) at the time of visit 2 simultaneously with the MRIs order allocation.

The randomization scheme will allocate subjects to the two P03277 treatment arms (0.05 or 0.1 mmol/kg BW) in a 1:1 ratio for the first subset of subjects and to the four P03277 treatment arms (0.025, 0.05, 0.1 or 0.2 mmol/kg BW) in a 1:1:1:1 ratio for the second subset of subjects. The P03277 will be injected at a rate of 2 mL/second.

The same dose of MultiHance®, 0.1 mmol/kg BW by single IV injection at a rate of 2 mL/second, will be injected to all subjects.

The randomization will be done via IWRS with a stratification factor for the subset 2: presence of brain metastasis (yes/no) and performed in blocks to prevent unequal treatment allocation. For the subset 2, subjects with brain metastasis will be included at a minimum of 20% in each dose group of P03277.

The study design and the injection of the IMPs require identifying before the study start, two separate teams in each study site. One will manage the blinded data and another one will be unblinded and will be in charge of the IMPs preparation and administration. The unblinded staff will have to document in a separated subject's file all the unblinded information related to the IMPs and will have to complete a dedicated eCRF pages with restricted access.

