## 9.2 Imaging Protocol

### 9.2.1 *MR equipment*

The procedure will be performed using a MRI scanner that can perform the required pulse sequences with a dedicated head coil or a spine coil. MRI units with 1.5T or 3T magnetic field will be used, regardless of the manufacturer. The following information must be recorded: the manufacturer, model, software version, and field strength of the MRI device.

For a single subject, it is mandatory to use the same MR equipment for the two MRI examinations required by the protocol.

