### 5.2.2. Protocol Deviations

As per International Conference on Harmonization (ICH) E3 guideline [2], a protocol deviation is any change, divergence or departure from the study design or procedures defined in the protocol, with or without impact to the subject safety or the efficacy assessments. Protocol deviations are displayed in the Clinical Study Report (CSR) as a metric of the feasibility and reliability of the study. The list of protocol deviations is presented in the table below and can be updated if necessary before breaking the blind. Protocol deviations will be gathered from monitoring files, clinical database and external vendors of off-site data (imaging, laboratory data, ECG...).

Protocol deviations will be split in major and non major deviations. A major deviation is defined as a deviation having an impact on the primary criteria. A first categorisation is done in this document, then final categorisation will be done before breaking the blind. The decision will be duly described in the meeting minutes.

The deviations are listed in the table below:

Category	Description	Source	Status
Inclusion criteria not met/Non inclusion criteria met	Subject not having reached legal majority age	Clinical data base	Non major
	Subject not presenting, at the time of inclusion, with known or highly suspected focal areas of disrupted Blood Brain Barrier (BBB) (e.g., primary and secondary tumors, focal inflammatory or demyelinating disorders) including at least one expected enhancing lesion of minimum 5 mm (long axis). This lesion must have been detected on a previous imaging procedure (computerized Tomography (CT) or MRI)	Clinical data base	Major
	Subject not scheduled for a routine CNS contrast-enhanced MRI examination for clinical reasons or not agreeing to have a second contrast-enhanced MRI examination for the purpose of the study	Clinical data base	Non major
	Subject not able or not willing to participate to the study	Clinical data base	Non major
	Subject not having provided his/her consent to participate in writing by dating and signing the informed consent prior to any study related procedure being conducted	Clinical data base	Non major

CONFIDENTIAL

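### A change of field strength or scanner between a subject's two exams is graded Non major, and a gap below the 2-day minimum has no deviation row, so such pairs can stay in the per-protocol primary analysis

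*SAP*

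**What the plan says.** Protocol 9.2.1 permits a mix of scanners across the study: "MRI units with 1.5T or 3T magnetic field will be used, regardless of the manufacturer". Within a subject it is strict: "For a single subject, it is mandatory to use the same MR equipment for the two MRI examinations required by the protocol".

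Protocol 5.3.1 has the two MRI visits "separated by a wash out period of 2 days minimum up to 14 days". Protocol 3.2 explains both limits. The lower one is "2 days to avoid carryover effects but", and the sentence goes on to an upper limit meant to keep disease progression or lesion change out of the comparison.

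SAP 5.2.2 states the grading principle: "A major deviation is defined as a deviation having an impact on the primary criteria". Its table then contains:

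- "Two different magnetic field strength used for both assessments": Non major.
- "Two different MRI machines used for both assessments": Non major. Different manufacturer, model and software version each have their own row, also Non major.
- An interval above 14 and up to 21 days: Non major. "Time between the two MRI procedures is strictly greater than 21 days": Major.
- No row for an interval below 2 days.

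SAP 5.2.2 excludes from the PPS only subjects with at least one Major deviation, and SAP 5.5.1 runs the primary analysis on the PPS.

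**The concern.** The primary criterion is the lesion signal minus the healthy-tissue signal, divided by the SD of background noise. Each term is read from the scanner's image, so the value depends on the machine as well as on the contrast agent. If a subject is imaged at 1.5T with one agent and at 3T with the other, the paired difference carries both effects and they cannot be separated. Protocol section 1 justifies the cross-over by the intra-subject comparison it allows for the primary criterion, and the same-equipment rule protects that comparison.

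The short interval raises a related problem. The protocol sets a lower limit specifically against carryover, yet a breach of it has no status in the table that decides who is in the primary analysis set.

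**Working it through.** This is mainly a comparison of texts. The sample-size figures do not bear on it.

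**1. Do the equipment rows fit the SAP's own definition of Major?** The test is impact on the primary criterion. SAP 5.5.2.3 tabulates CNR separately for 1.5T and 3.0T, so the SAP itself treats field strength as relevant to CNR. The same table grades two other threats to the comparability of a pair as Major: an injection-to-acquisition time that differs by more than 30 minutes between the exams, and a gap of more than 21 days. A change of field strength is at least the same kind of threat, so its Non major status is inconsistent with the definition and with these rows.

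**2. Are both sides of the interval window covered?** The protocol window is 2 to 14 days. Above it, the table has two graded rows. Below it, there is none.

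**3. Does another part of the plan deal with such pairs?**

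- Primary model (SAP 5.5.1.2 and 5.5.1.3): contrast agent, period and pre-contrast CNR, with a random subject effect. There is no scanner or field term.
- FAS analysis (5.5.2.1): restricted to subjects with CNR at both exams; mismatched pairs are kept.
- Pooled-reader analysis (5.5.2.2): same PPS, so they are kept.
- ROI-placement sensitivity analysis (5.5.2.4): selects on ROI position, not on equipment.
- Summaries by field strength (5.5.2.3): descriptive only.

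No planned analysis removes them.

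**4. When does excluding mismatched pairs help precision?** Assume n pairs with paired-difference SD s, a fraction f of them mismatched, and a mismatch that shifts the difference by k·s with either sign equally likely.

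- Keep them: SE² = s²(1 + f·k²)/n.
- Exclude them: SE² = s²/[n(1 − f)].
- Equal when 1 + f·k² = 1/(1 − f), so k = 1/√(1 − f).

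For f = 5%, k = 1/√0.95 = 1.03. For f = 10%, k = 1/√0.90 = 1.05. The break-even is therefore about 1 SD. If the planning SD of 3.01 is the SD of the paired difference (the documents do not say whether it is), that is 1.03 × 3.01 = 3.09 and 1.05 × 3.01 = 3.16 CNR units. Below that shift, keeping the pairs is slightly more precise; above it, excluding them is.

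**5. When is there bias?** If a share q of the mismatched pairs favours P03277, bias = f(2q − 1)·k·s. With q = 0.5 it is zero. With f = 10%, k = 1 and s = 3.01, it is 0.10 × 0.5 × 3.01 = 0.15 units at q = 0.75, and 0.10 × 3.01 = 0.30 units at q = 1. The values of f, k and q are assumptions; none is in the documents.

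**The case against.** The best reply is that the table is not final. SAP 5.2.2 calls it a first categorisation, allows the list to be updated, and places the final grading before the blind is broken, with minutes. It also has a Major row for departures from the imaging protocol with major impact on the primary criterion, and the same-equipment rule sits in the protocol's imaging section. A reader might infer that mismatched pairs will enter the primary analysis; the documents support only that they can. The reply does not remove the point, however. The catch-all row rests on judgement, while the specific rows already say Non major. Its companion row, for departures with an impact that is not called major, is Non major as well, which itself conflicts with the SAP's definition.

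Two features soften the harm. Each period's own pre-contrast CNR is a covariate, and Protocol 9.2.2 requires the same settings before and after injection; together these absorb part of a scanner offset or of residual contrast, though not a scanner effect on the size of enhancement. Order is randomised, so mismatch should mainly add variance, and the documents suggest no reason for imbalance between agents.

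A short gap is probably rare. Visit 3 falls one day after visit 2, and visit 4 is scheduled from day 2. SAP 5.6.1.1 also tabulates the time between injections, so a breach could be seen, but it would have no status.

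Finally, nothing in the documents shows that two machines of the same model and field strength change CNR enough to require automatic exclusion. That stands, and the fix allows for it.

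**Conclusion.** The point holds as an inconsistency in the rules that define the primary analysis set. The field-strength row contradicts the SAP's definition of Major and its treatment of comparable threats. The manufacturer, model, software and machine rows are unreconciled with a mandatory protocol rule. The carryover side of the interval window has no grade. As written, affected pairs can stay in the PPS, and no analysis shows the result without them.

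The size cannot be stated. A reader might infer a definite loss of power from keeping these pairs, or a biased dose comparison. Neither is supported: the frequency and the CNR effect of mismatch are not given, excluding pairs also costs subjects, and exclusion gains precision only above a shift of about 1 SD of the paired difference. That break-even assumes shifts of random sign. Bias needs mismatch spread unevenly between agents. The case for the change is comparability of the pairs and consistency with the plan's own rules, not a demonstrated gain in power. It should be made because it is cheap and the SAP leaves room for it.

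**What to change.** Before the blind is broken, at the final categorisation:

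1. Set the different-field-strength row to Major.
2. Reconcile the manufacturer, model, software and machine rows with Protocol 9.2.1 and with the SAP's definition of Major, and record the reason for each status. State which row prevails when a specific equipment row and the general imaging-protocol row both apply.
3. At minimum, repeat the primary analysis without any pair acquired on mismatched equipment.
4. Add a row, with a status, for an interval below the protocol minimum.

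The cost is a table edit, a minuted decision and one further run of the existing model. The PPS loses the few affected subjects; they remain in the FAS analysis. That analysis also admits unmatched lesions, so it does not isolate the effect of equipment, which is why item 3 is needed.

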## FORM

[REDACTED]

## STATISTICAL ANALYSIS PLAN N° GDX-44-004

Page 24 / 60

VERSION 1.0

DATED: 09JAN2018

[REDACTED]

	Prior to MRI blood sample for central laboratory assessment is not drawn before contrast media administration	Clinical data base	Non major
	Prior to MRI urinalysis is not performed before contrast media administration	Clinical data base	Non major
	1 day post MRI blood sample for central laboratory assessment is not drawn the day after contrast media administration	Clinical data base	Non major
	1 day post MRI urinalysis is not performed the day after contrast media administration	Clinical data base	Non major
	Before injection vital sign is not taken before contrast media administration	Clinical data base	Non major
	45-minute after injection vital sign is not taken between 30 and 60 minutes after contrast media administration	Clinical data base	Non major
	Between 2 and 4 hours after injection vital sign is not taken between 2 and 4 hours after contrast media administration	Clinical data base	Non major
	1 day post MRI vital sign is not taken the day after contrast media administration	Clinical data base	Non major
	Before injection ECG is not performed before contrast media administration	Clinical data base	Non major
	45-minute after injection ECG is not performed between 30 and 60 minutes after contrast media administration	Clinical data base	Non major
	Between 2 and 4 hours after injection ECG is not performed between 2 and 4 hours after contrast media administration	Clinical data base	Non major
	1 day post MRI ECG is not performed the day after contrast media administration	Clinical data base	Non major
GCP deviation	ICF deviation	Monitoring	Non major
	Source document management not appropriate	Monitoring	Non major

Subjects presenting at least one protocol deviation with a status major will be excluded from the PPS.

Frequency and percentages of subjects with protocol deviations will be presented breaking down by status (major/non major).

Subjects with major protocol deviations throughout the study causing exclusion from the PPS will be presented by contrast agent and globally on the Extended Set for each subset separately: subjects with at least one major protocol deviation and subjects with each major protocol deviation. Non major protocol deviations will follow the same disposition.

The tables and listings that will be displayed are detailed in Sections 6.1.1.2 and 6.2.2.

CONFIDENTIAL	FORM	
STATISTICAL ANALYSIS PLAN N° GDX-44-004		Page 25 / 60
VERSION 1.0      DATED: 09JAN2018		

### 5.3. Measurements of study drug compliance

The subject's theoretical dose of contrast agent calculated for each subject was given by Interactive Web Response System (IWRS). The subject's actual dose administered was recorded in the electronic Case Report Form (eCRF). When the actual dose was different from the theoretical dose, the reason had to be given and recorded in the eCRF. Subjects with a difference between theoretical and actual volumes of study product will be described using the FAS. The difference in mL and in % will be presented for these subjects by descriptive statistics. The reasons of the differences will be listed only.

The table and the listing that will be displayed are detailed in Sections 6.1.1.6 and 6.2.5.

#### 5.4. Demographic and Other Baseline Characteristics

Demographic data will be described using the FAS, the PPS and the Safety Set, medical history and previous medications will be described using the FAS and the Safety Set whereas other baseline characteristics will be described using the FAS only.

For tables described on the FAS (and the PPS if any, see Section 5.2.1), 5 columns will be displayed: "P03277 0.025 mmol/kg", "P03277 0.05 mmol/kg", "P03277 0.1 mmol/kg", "P03277 0.2 mmol/kg" and "Total", the dose being the one allocated by the randomization (either at the 1st or the 2nd period).

For tables described on the Safety Set, 7 columns will be displayed: "P03277 0.025 mmol/kg", "P03277 0.05 mmol/kg", "P03277 0.1 mmol/kg", "P03277 0.2 mmol/kg", "Total P03277", "MultiHance®" and "Total", the dose being the one actually received (either at the 1st or the 2nd period). It corresponds to the disposition of safety tables, except for tables of AEs in which period (MRI 1 and MRI 2) will appear also.

### 5.4.1. Demographic data

Demographic characteristics collected at screening, except for weight at Visit 2 and Visit 4, include the following parameters:

- Age (years) calculated using the following formula: (inclusion visit date - birth date) / 365.25.
- Gender: Male; Female.
  - If Female, contraceptive status: Woman of childbearing potential using effective contraception; Post-menopausal (with minimum 12 months of amenorrhea); Surgically sterilized.
- Weight at Visit 2 and Visit 4 (kg).
- Height (cm).
- Body Mass Index (BMI) at Visit 2 and Visit 4: 
$$BMI = \frac{BodyWeight(Kg)}{Height(m)^2}$$

where height is in m and weight in kg. BMI will be displayed as a quantitative variable only.
- Ethnicity: Hispanic or Latino; Not Hispanic nor Latino.

CONFIDENTIAL	FORM	
STATISTICAL ANALYSIS PLAN N° GDX-44-004		Page 26 / 60
VERSION 1.0      DATED: 09JAN2018		

- Race (multiple choices): American Indian or Alaska Native; Asian; Black or African American; Native Hawaiian or other Pacific islander; White; Other.

The tables and the listing that will be displayed are detailed in Sections 6.1.1.4 and 6.2.4 respectively.

### 5.4.2. Study disease

Study disease is assessed by the imaging procedure documenting the study disease, the presence of brain metastasis or not and the diagnosis.

The most recent imaging procedure documenting at least one enhancing lesion with a size of minimum 5 mm will be described: Computed Tomography (CT), MRI, other. Time from this procedure to the first injection of contrast agent will be presented in months: (injection date - procedure date) / 30.4.

Presence of brain metastasis will be described.

Study disease diagnosis will be coded in Primary System Organ Class (SOC) and Preferred Terms (PT) using the Medical Dictionary for Regulatory Activities (MedDRA) dictionary version 20.1. The table will be sorted by descending global frequencies of SOC and by descending global frequencies of PT within each SOC and presented by presence of brain metastasis or not.

The tables and the listing that will be displayed are detailed in Sections 6.1.1.4 and 6.2.4 respectively.

### 5.4.3. Risk factors

Not applicable.

#### 5.4.4. Medical history and concomitant diseases

Medical history collected at screening visit will be classified as follows:

- **Past diseases** are defined as diseases which are not “ongoing” at the time of the assessment of the subject’s medical history.
- **Concomitant diseases** are defined as diseases which are “ongoing” at the time of the assessment of the subject’s medical history.

Medical history will be coded in Primary SOC and PT using the MedDRA dictionary version 20.1. Data on medical history recorded at screening visit will be summarized according to SOC and PT.

The table will be sorted by descending frequency of SOC and, within each SOC, by descending frequency of PT.

The tables and the listing that will be displayed are detailed in Sections 6.1.1.4 and 6.2.4 respectively.

CONFIDENTIAL	FORM	
STATISTICAL ANALYSIS PLAN N° GDX-44-004		Page 27 / 60
VERSION 1.0      DATED: 09JAN2018		

